Title page

**Is Endotracheal Tube Use Mandatory in Patients Undergoing Nasal Septum Surgery?
Randomized, Controlled, Prospective Clinical Trial**

[name], Asst. [name] of Anesthesiology and Reanimation, Inonu University Medical Faculty, Malatya, Turkey

[name], Asst. [name] of Anesthesiology and Reanimation, Inonu University Medical Faculty, Malatya, Turkey

[name], Asst. [name] of Anesthesiology and Reanimation, Inonu University Medical Faculty, Malatya, Turkey

[name], [name] of Anesthesiology and Reanimation, Inonu University Medical Faculty, Malatya, Turkey

Address all correspondence to:

[name], Asst. [name] of Anesthesiology and Reanimation, Inonu University Medical Faculty, Malatya, Turkey

Mail: [contact]

[contact]

Protocol

This study is approved in Malatya Clinical Research Ethics Committee with the protocol code of 2018-165 and carried out at Department of Anesthesiology, Inonu University Medical Faculty in accordance with the criteria of Helsinki Agreement.

The study is planned as a prospective, randomized clinical trial. For randomization, the patients will be assigned to the study groups entirely by chance, and selection bias was prevented. MedCalc for Windows, version-16 statistical software (medcalc.com.tr.) will be used. A total of 80 patients with elective nasal septum surgery will be randomly assigned to the groups of Supreme LMA (Group L, n = 40) and ETT (Group E, n = 40).

Patients who agreed to participate voluntarily were informed about the potential risks and predictable outcomes of the study. The study will be performed on 80 patients between 18-65 years old, American Society of Anesthesiologists (ASA) I-II group planned for elective nasal septum surgery. Preoperative anesthesia evaluation (I) higher than ASA II (II) Patients with severe respiratory, hepatic or renal dysfunction (IV) Patients with history of allergy to anesthesia medications (V) of neurology and psychiatry patients (VI) Body mass index (BMI) of 30 Patients with obstructive airway history (cervical spine pathology, modified Mallampati grade 4 or thyromental distance <65 mm, VIII) will be excluded from the study who had a high risk of regurgitation or aspiration.

Patients who opened their eyes with eye, breathing regularly, respiratory rate was 12-20 / min, oxygen saturation greater than 95% will be extubated and taken to the recovery room (PACU).

Outcome Measures

In Group L and E, oropharyngeal leak pressures will be measured while the head will be in neutral position. The flowmeter O₂ current will be set at 3 L / min and the expiratory valve will be closed. When an investigator who did not know which type of airway device was placed, another researcher looked at the current pressure value from the aneroid manometer and confirmed that the pressure remained constant (pressure gauge stability test). This value was recorded as the value of oropharyngeal leakage pressure. To prevent lung exposure to barotrauma, the expiratory valve was opened when the peak inspiratory pressure reached 40 cmH₂O, and the test will be terminated.

At the end of the surgery, in Group L and E, the presence of blood will be observed through a tubular fiberoptic bronchoscope. Posterior oropharynx will be carefully aspirated at the end of surgery in patients with endotracheal tube. After extubation, presence of blood around ETT cuff and distal blood will be examined. In the presence of blood, a four-scale scale will be used at the level of glottis-trachea and distal trachea. (1 = no, 2 = mild, 3 = moderate, 4 = severe). Mean arterial pressure (MAP), heart rate (HR), and peripheral oxygen saturation (SpO₂) immediately prior to anesthesia induction, 5, 15, 30, 45, 60 after confirmation of airway placement 75. EtCO₂ will be recorded per minute and every 15 minutes during the operation. Demographic data, duration of surgery and total anesthesia duration will be recorded.

Orogastric tube placement; very easy, easy, difficult, very difficult in the form of a 4-point scale will be used.

Pharyngolaryngeal adverse events (laryngospasm, bronchospasm, nausea, vomiting, coughing, desaturation (SpO₂ <94) and re-intubation need will be observed in the operation room and PACU at 5, 15, 25 and 45 min. Sore throat, nausea, vomiting, dysphonia and dysphagia will be evaluated and recorded at 2, 4, 6, 12 and 24 hours postoperatively. Postoperative adverse effects will be evaluated as follows: laryngospasm; airway obstruction due to muscle rigidity in the chest and abdomen, Bronchospasm; especially during expiration, increased respiratory effort and wheezing. Dysphonia; difficulty in speech because of difficult speech or pain. Difficulty in swallowing; difficulty in swallowing or painful swallowing.

Sore-throat; it was defined as constant pain felt independently of swallowing. The evaluation was made with 0 ile10 numerical pain rating scale (NRS: Numeric Rating Scala). According to NRS, sore throat score will be evaluated as; 0-1: none, 2-4: mild, 5-7: intermediate and 8-10: severe.

5 point scale was used to determine the severity of nausea / vomiting. (0 = no nausea, 1 = mild nausea, 2 = moderate nausea, 3 = vomiting less than 2 times per hour, 4 = vomiting more than 2 times per hour).

Cough; cough in the postoperative period (less than 5 coughs will be ignored within the first minute after removal of the mask or tube, more than 5 coughs will be counted),

Statistical Analyzes

Type I error (alpha) 0.05, the power of the test (1-beta) 0.9, the primary output variable in the air (glottis / trachea) for the amount of blood effect of 0.71 and the alternative hypothesis (H1) is two-way to be found a significant difference using this test A total of 80 patients were required, with a minimum sample size of 40 in each group (*Kaplan A, Crosby GJ, Bhattacharyya N. Airway Protection and the Laryngeal Mask Airway in Sinus and Nasal Surgery. Laryngoscope 114: April 2004.*)

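### The primary blood grade can differ between arms because of how it is obtained: suction and a cuff examination are written for the tube arm only, and no rule says which observation sets the grade

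*Combined protocol and SAP*

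**What the plan says.** The Statistical Analyzes section sizes the trial on the "primary output variable in the air (glottis / trachea) for the amount of blood effect of 0.71", with 40 patients per arm.

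The Outcome Measures section is the only place that says how this is measured:

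- Both arms: "At the end of the surgery, in Group L and E, the presence of blood will be observed through a tubular fiberoptic bronchoscope".
- Tube arm only: "Posterior oropharynx will be carefully aspirated at the end of surgery in patients with endotracheal tube".
- Tube arm only: "After extubation, presence of blood around ETT cuff and distal blood will be examined".
- Then the grade: when blood is present, "a four-scale scale will be used at the level of glottis-trachea and distal trachea", running from 1 (none) to 4 (severe).

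For the mask arm (Group L) the plan states no matching suction and no inspection of the removed device. It does not say whether the scope goes through or beside the device, whether the scope comes before or after suction, or whether the scope view, the removed cuff or both determine the grade.

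**The concern.** Randomization balances the patients, but it cannot balance a measurement that is made differently in each arm. Here the unequal steps lie close to the quantity being graded. If suction comes before grading and clears blood that would have been graded, the Group E grade falls and the mask looks worse. If blood picked up on the cuff as the tube is drawn out is counted, the Group E grade rises and the mask looks better. The trial asks whether the tube can be dispensed with, so either effect would bear on its main conclusion.

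**Working it through.** **1. The possible scope routes, set side by side.**

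- *Through the device in both arms.* In Group L the scope emerges above the glottis and can see it. In Group E the tube lies in the glottis and the scope emerges beyond the cuff, so the first airway seen is the trachea. Anything recorded for the Group E glottis would have to come from elsewhere, and the removed cuff is the only other look described.
- *Beside the tube in Group E.* Blood above the Group E seal would be set against blood below the Group L seal.
- *After removal in both arms.* Only Group E has a written suction step before this. Removal also waits for "Patients who opened their eyes with eye, breathing regularly", so the inspection would be made in waking patients.

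No route by itself makes the glottis-trachea grade alike in the two arms. A stated rule is needed.

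**2. The plan's own figure.** Inputs from Statistical Analyzes: d = 0.71, two-sided alpha 0.05, power 0.90, 40 per arm.

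- Normal approximation: n = 2(1.960 + 1.282)² / 0.71² = 21.01 / 0.504 = 41.7, so 42 per arm; a t-test needs 43.
- Power at 40 per arm: noncentrality 0.71 × √(40/2) = 3.175 on 78 df, giving 0.880.

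The stated 40 is close to this. The small shortfall is a separate matter.

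**3. A method-only shift on the SD scale.** The documents give no shift, so b is assumed. With equal blood in both arms the noncentrality is b√20. With a true effect of 0.71 the observed effect is 0.71 ± b.

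| b (SD) | False difference, equal arms | Power, shift against 0.71 | Power, shift with 0.71 |
|---|---|---|---|
| 0 | 5.0% | 0.880 | 0.880 |
| 0.1 | 7.3% | 0.769 | 0.947 |
| 0.2 | 14.3% | 0.615 | 0.980 |
| 0.3 | 26.3% | 0.441 | 0.994 |

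At b = 0.05 the false-difference rate is 5.6%. Shifts below about 0.1 SD matter little.

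**4. The same on the four-point scale.** Grades are assumed equal in both arms before the method acts. The test is a tie-corrected Mann-Whitney, 40 v 40, with 400,000 simulated trials per case. Suction lowers the grade by one in 10%, 25% or 50% of Group E patients with blood. Cuff pick-up moves 10%, 20% or 30% of clean Group E patients from grade 1 to 2. In the combined row suction acts first and pick-up then acts on those who are clean, pairing the settings in order.

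| False difference | Grades 50/30/15/5% | Grades 70/20/7/3% |
|---|---|---|
| Suction alone | 6%, 10%, 28% | 5%, 8%, 18% |
| Cuff pick-up alone | 6%, 10%, 17% | 9%, 21%, 39% |
| Both together | 5%, 5%, 5% | 7%, 12%, 18% |

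For scale: with grades 50/30/15/5% the mean is 1.75 and the SD 0.887. Suction in 25% shifts the mean by 0.25 × 0.50 / 0.887 = 0.14 SD. Pick-up in 20% shifts it by 0.20 × 0.50 / 0.887 = 0.11 SD the other way.

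**The case against.** The scope and the scale are common to both arms, and the text may be no more than a terse translation. By sentence order the scope comes before the suction. The suctioned site, the posterior oropharynx, is not a graded level, and with the cuff still inflated suction there does not remove blood already below it. The cuff is not a named level of the scale either, so its entry into the grade is an inference from silence. The compound label glottis / trachea can be read functionally, as blood that got past the device: glottis in Group L, trachea in Group E. That contrast is close to the trial's question and may be intended. Clearing the pharynx before extubation can also be seen as part of the tube strategy. Finally, no shift or grade distribution above comes from the documents, and the two mechanisms can offset each other.

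All of this stands as a limit on how far the point goes. It does not remove the point. Sentence order is not a stated sequence, the functional reading is nowhere written down, and nothing says that the scope view alone sets the grade. An investigator who follows the written steps can properly grade Group E after suction, or with the cuff in hand, and has no counterpart for either in Group L.

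**Conclusion.** The point holds as a gap in the definition of the primary measurement, combined with steps written for one arm only. It is more than missing detail, because following the text can yield different measurements in the two arms. It is worth fixing; its effect on the result is unknown. The figures of 7% to 26% rest wholly on assumed shifts of 0.1 to 0.3 SD, and with both mechanisms acting the rate ranged from 5% (full cancellation) to 18% under the assumed grade distributions.

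A reader might infer more, and the documents do not support it:

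- *That the two grades are certainly different measurements because a scope through the tube cannot show the glottis.* This depends on a scope route that the plan does not state.
- *That the bias has a known direction, for or against the mask.* Suction and cuff pick-up push opposite ways, and it is not established that either enters the grade.
- *That the primary outcome should move to the distal trachea.* Blood may be rarer there, so the effect of 0.71 may not carry over and the sample size would need rechecking. Viewing that level in Group L also means passing the scope through an unprotected glottis in patients given no muscle relaxant, which could carry blood down or provoke a reaction in that arm only.

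**What to change.** Write one procedure for both arms:

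1. At the end of surgery, before any suction, cuff deflation or device removal, pass the scope through the device, with the route stated.
2. Grade the first airway seen beyond the device (glottis in Group L, trachea in Group E), defined in the protocol as blood that passed the device. Then grade the distal trachea.
3. Base the primary grade on this scope view only.
4. Suction the oropharynx in both arms, after grading.
5. Record blood on the removed cuff as a separate descriptive item that does not feed the grade.
6. Report the distal-trachea comparison, which the plan already collects, beside the primary result as a supporting analysis and not as its replacement.

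The cost is small. Group L gains a brief suction, and no examination is added. The price is that the Group E glottis above the cuff is not part of the grade, so the report should say that the primary outcome is blood past the device and not blood at one anatomical site.

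### Minor: sore throat, dysphonia and dysphagia have no preoperative value, so the protocol does not prevent persisting symptoms from being counted as postoperative adverse effects

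*Combined protocol and SAP*

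**What the plan says.** **Timing.** Under Outcome Measures, "Sore throat, nausea, vomiting, dysphonia and dysphagia will be evaluated and recorded at 2, 4, 6, 12 and 24 hours postoperatively". The first assessment of sore throat, dysphonia and dysphagia is therefore 2 hours after surgery.

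**Definitions.** For sore throat, "it was defined as constant pain felt independently of swallowing". It is graded on the raw 0–10 numerical scale: 0–1 none, 2–4 mild, 5–7 intermediate, 8–10 severe. Dysphonia and dysphagia are defined by present difficulty or pain. The three are listed among postoperative adverse effects, and none of the definitions mentions onset or change from before surgery.

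**Eligibility (Protocol section).** On inclusion: "The study will be performed on 80 patients between 18-65 years old, American Society of Anesthesiologists (ASA) I-II group planned for elective nasal septum surgery". The visible exclusions are ASA above II; "Patients with severe respiratory, hepatic or renal dysfunction"; drug allergy; neurology and psychiatry patients; body mass index; obstructive airway history ("Patients with obstructive airway history (cervical spine pathology, modified Mallampati grade 4 or thyromental distance <65 mm, VIII) will be excluded from the study"); and risk of regurgitation or aspiration. The numbering runs I, II, IV, V, VI, VIII.

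**Values before induction.** The plan sets "Mean arterial pressure (MAP), heart rate (HR), and peripheral oxygen saturation (SpO₂) immediately prior to anesthesia induction". For other background data, "Demographic data, duration of surgery and total anesthesia duration will be recorded". The Protocol section mentions a preoperative anaesthesia evaluation but does not say what it records about throat, voice or swallowing.

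**The concern.** An ASA I–II patient with a mild sore throat or a hoarse voice meets every visible entry criterion. If that patient arrives with a sore throat of 4 on the numerical scale and still has it at 2 hours, the plan as written grades it as mild sore throat under postoperative adverse effects. Nothing in the record would separate this patient from one whose symptom began with the airway device.

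The trial asks whether a tube is needed, and throat and voice symptoms are part of that comparison, each with five assessments. Symptoms present beforehand raise the event rate in both arms and pull the contrast towards no difference. If they fall unevenly between two arms of 40, nobody can see it or adjust for it, because a preoperative value cannot be reliably recovered afterwards. Haemodynamic and oxygenation variables do get a pre-induction value; these symptoms do not.

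**Working it through.** **1. The plan's own figure.** The Statistical Analyzes section gives 40 per group for blood at the glottis/trachea, from effect 0.71, two-sided alpha 0.05 and power 0.90. Reading 0.71 as a standardised difference:

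n per group = 2 × ((1.960 + 1.282) / 0.71)² = 41.7, so 42; power at 40 per group is 0.888.

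That is close to the stated 40 and 0.90. It concerns the primary outcome only. The plan states no power for throat symptoms, and this point does not depend on the figure.

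**2. Reading check.**
- Exclusion for a current throat, voice or swallowing symptom: none visible.
- Value before induction: only MAP, HR and SpO₂ are set at that time.
- First record: 2 h after surgery.
- Requirement that the symptom be new or worse: none.
- Adjustment for a baseline value in the analysis: none stated.

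**3. Size of the dilution.** Everything in this step except n = 40 and alpha = 0.05 is assumed. Let p be the rate of new symptoms and b the share with a pre-existing symptom, equal in both arms in expectation. If every pre-existing symptom persists and qualifies:

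observed rate = b + (1 − b)p, so observed difference = (1 − b) × (true difference).

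Power uses the arcsine approximation: h = 2·arcsin√p₁ − 2·arcsin√p₂, and power = Φ(h·√(40/2) − 1.960). With p = 40% v 15%:

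| b | observed rates | difference (points) | risk ratio | power |
|---|---|---|---|---|
| 0 | 40.0 v 15.0% | 25.0 | 2.67 | 0.73 |
| 2% | 41.2 v 16.7% | 24.5 | 2.47 | 0.69 |
| 5% | 43.0 v 19.3% | 23.8 | 2.23 | 0.65 |
| 10% | 46.0 v 23.5% | 22.5 | 1.96 | 0.57 |
| 20% | 52.0 v 32.0% | 20.0 | 1.63 | 0.45 |

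Worked line for b = 10%: 0.10 + 0.90 × 0.40 = 0.46 and 0.10 + 0.90 × 0.15 = 0.235; h = 0.4785; 0.4785 × 4.472 = 2.140; Φ(2.140 − 1.960) = 0.57.

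With other assumed rates, 50% v 20%, power falls from 0.82 to 0.76, 0.70 and 0.58 at 5%, 10% and 20%. The direction is the same.

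**4. Chance imbalance.** With both arms Binomial(40, b), the probability that they differ by 4 or more patients with a pre-existing symptom is 0.8% at b = 2%, 7% at 5%, 19% at 10% and 33% at 20%. Four extra such patients are not four extra events, since some would have developed the symptom anyway: the net excess is 4 × (1 − 0.40) = 2.4 events at a 40% rate and 4 × (1 − 0.15) = 3.4 at 15%.

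**The case against.** **These are not the primary outcome.** This stands. Sample size and power are set on blood in the airway, so the power figures above describe the loss of sensitivity in a further outcome. They do not show a shortfall against any promised target.

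**Randomisation takes care of it.** Partly right. A reader might infer that the results would be biased towards one device, or that an uneven start could produce a spurious finding. The documents do not support that. Allocation is random, pre-existing symptoms balance in expectation, and an ordinary two-arm test already allows for chance differences, so type I error is not inflated. Randomisation does not remove the dilution, and it does not make a particular imbalance visible.

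**The text does not say that old symptoms are attributed to the device.** Correct. A reader might take it that they definitely are. The plan speaks of postoperative adverse effects and gives no rule for a symptom already present. What can be said is that nothing prevents them from being counted.

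**The eligibility list is incomplete as printed.** Items III and VII are absent, and a relevant criterion could have been lost. The content of the preoperative evaluation is also undescribed. It therefore cannot be asserted that such patients are certainly admitted, only that no visible criterion keeps them out.

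**The prevalence may be very low.** This is a fair limit. Elective ASA I–II patients may rarely arrive with these symptoms. A pre-existing sore throat must also be constant, independent of swallowing, still present at 2–24 h and at least 2 on the scale. At 2% prevalence the loss is small (0.73 to 0.69).

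**Cough.** A reader might extend the point to cough. It does not fit: cough is observed in the operating room and recovery room, and its counting rule is tied to the first minute after device removal, which largely reflects emergence.

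**Conclusion.** The point holds, as a minor one, for sore throat, dysphonia and dysphagia. First assessment at 2 hours, definitions that ignore onset, no visible exclusion and no preoperative record together leave the plan unable to separate new symptoms from persisting ones. The consequence is inflated rates in both arms, a contrast diluted towards no difference, and imbalance that can be neither seen nor corrected.

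The size depends on a prevalence that the documents do not give. Under the assumed 40% v 15%, it runs from slight at 2% to substantial at 20%. Those figures are an upper bound for each prevalence, because they take every pre-existing symptom to persist and qualify. The validity of the randomised comparison and the primary analysis are not in question.

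**What to change.** At the existing preoperative anaesthesia evaluation, before randomisation, record the sore throat score on the same 0–10 scale, and dysphonia and dysphagia with the same definitions as after surgery. Then state in the plan that only new or worsened symptoms count as postoperative adverse effects, and define worsened in advance (for sore throat, for example, a higher severity band than before surgery). Adjusting the analysis for the baseline value is an alternative.

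This recovers much of the loss even in an unfavourable case. If no patient with a pre-existing symptom could be seen to worsen, 10% prevalence would give 0.90 × 40% = 36% v 0.90 × 15% = 13.5%. Then h = 0.5345, 0.5345 × 4.472 = 2.390, and power = Φ(2.390 − 1.960) = 0.67, against 0.57 with no baseline.

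The cost is about a minute of questions per patient at a visit that already takes place, and one line on the case-report form. No patients are lost. It has to be in place before enrolment, because the value cannot be obtained reliably after surgery.

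### Dysphonia is defined circularly and without a voice sign, so hoarseness can be missed and difficult speech after nasal surgery counted, which dilutes any tube-versus-mask voice difference

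*Combined protocol and SAP*

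**What the plan says.** The Outcome Measures section sets the follow-up for these symptoms: "Sore throat, nausea, vomiting, dysphonia and dysphagia will be evaluated and recorded at 2, 4, 6, 12 and 24 hours postoperatively". It then introduces the definitions with "Postoperative adverse effects will be evaluated as follows". The three that matter here are:

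- Voice: "Dysphonia; difficulty in speech because of difficult speech or pain".
- Swallowing: "Difficulty in swallowing; difficulty in swallowing or painful swallowing".
- Sore throat: "it was defined as constant pain felt independently of swallowing", scored on a 0 to 10 numeric scale and banded as "0-1: none, 2-4: mild, 5-7: intermediate and 8-10: severe".

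Dysphonia has no severity scale, no voice-quality criterion and no rule for setting aside speech trouble caused by the operation. All patients have elective nasal septum surgery and are "randomly assigned to the groups of Supreme LMA (Group L, n = 40) and ETT (Group E, n = 40"). The Statistical Analyzes section covers only the sample size for blood at the glottis and trachea. It names no test for dysphonia and claims no power for it.

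**The concern.** A tube passes between the vocal cords and a mask sits above them, so voice change is a natural secondary comparison in a trial that asks whether the tube is needed. The definition should pick up a change in the voice and leave out what the nasal operation does to speech. The written rule does neither.

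- It omits the sign of interest. Hoarseness in a patient who talks freely and without pain does not meet it.
- It admits something else. Speech that is difficult because the nose is blocked or sore does meet it, and assessment starts 2 hours after nasal surgery.

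At stake is a secondary result that could report the devices as similar for voice because the measure is unspecific.

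**Working it through.** **Reading the definition.** It has one required element, difficulty in speech, and two permitted causes, difficult speech or pain. The first cause restates the required element and so restricts nothing. Applied to three patients:

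| Patient | Difficulty in speech? | Counted as dysphonia? |
|---|---|---|
| Hoarse, speaks easily, no pain | No | No |
| Speech difficult from a blocked or sore nose, voice normal | Yes | Yes |
| Throat pain, speech unaffected | No | No |

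The first two rows are the defect. The third shows that pain alone does not qualify.

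**The plan's own figure.** There is none for dysphonia. The sample size is set for blood at the glottis and trachea, with "Type I error (alpha) 0.05, the power of the test (1-beta) 0.9", a two-sided alternative and an effect of 0.71. Taking 0.71 as a standardised difference (my reading), n per arm = 2 × (1.960 + 1.282)² / 0.71² = 41.7, so 42 against the stated 40. Power at 40 per arm is 0.888 by the normal approximation. The plan's figure is thus about reproduced, and nothing in it depends on the dysphonia definition.

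**Size of the dilution (illustration).**

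From the documents: 40 patients per arm and alpha 0.05.

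Assumed: device-related dysphonia d of 10% with the mask and 35% with the tube; a surgical background b, equal in both arms and independent of the device effect; one yes/no result per patient; an uncorrected chi-square test.

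Observed rate = 1 − (1 − d)(1 − b), so the observed difference is (0.35 − 0.10)(1 − b) = 0.25(1 − b). For b = 20%:

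- mask: 1 − 0.90 × 0.80 = 28%
- tube: 1 − 0.65 × 0.80 = 48%
- difference: 20 points

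Power is found by summing exact binomial probabilities over all pairs of counts at which the test rejects.

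| Background b | Mask | Tube | Difference (points) | Power |
|---|---|---|---|---|
| 0% | 10.0% | 35.0% | 25.0 | 79% |
| 5% | 14.5% | 38.3% | 23.8 | 69% |
| 10% | 19.0% | 41.5% | 22.5 | 60% |
| 20% | 28.0% | 48.0% | 20.0 | 46% |
| 30% | 37.0% | 54.5% | 17.5 | 37% |
| 40% | 46.0% | 61.0% | 15.0 | 29% |

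With a smaller assumed device difference, 10% v 30%, power is 63% with no background and 32% at a 20% background. The table covers only the surgical cases let in. Any loss from uncounted hoarseness would come on top and is not quantified.

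**The case against.** The strongest reply is that this is loose wording on one secondary symptom. The symptom carries a voice term as its name and follows directly on a list of pharyngeal and laryngeal events, so a sensible assessor might not record nasal-sounding speech. The text also looks translated, so the circularity may be a language slip. The device and background rates are assumed, and at a 5% background the loss is about 10 points of power. No power was promised for this outcome.

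Much of this stands. It limits the point to a non-primary outcome and makes the power figures illustrative. It does not repair the definition: assessors are given a written rule, the rule names no voice sign, and whether they would depart from it is unknown.

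A reader might infer three stronger things that the documents do not support:

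- **That pain alone counts as dysphonia.** Difficulty in speech is required; pain is only one possible cause of it.
- **That one painful throat is scored three times.** Sore throat is worded as separate from swallowing. A constant pain that also hinders speech and swallowing could be recorded under all three names, but no sum, count or composite is planned.
- **That surgical speech trouble is booked as device harm.** The text speaks of postoperative adverse effects and attributes none to the device. With the same type of surgery in both randomised arms, such trouble should balance on average.

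**Conclusion.** The concern holds as a defect in one secondary outcome definition. Taken literally, the rule misses hoarseness without difficulty or pain and admits difficult speech after septum surgery in both arms. The direction is dilution: a true voice difference becomes harder to see, and none is created on average. Under the assumed 10% v 35%, power falls from 79% to between 69% and 29% as the background rises from 5% to 40%. Where the trial would lie in that range cannot be told from the documents, because they give no dysphonia rate and no rate of speech trouble after this surgery. The primary outcome, the sample size and the randomised comparison are untouched. The overlap of pain across the voice, swallowing and sore-throat definitions is not an error by itself, and splitting painful from difficult swallowing would be a matter of preference.

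**What to change.** Define dysphonia as new hoarseness or a change in voice quality since before surgery, and state that nasal-sounding speech from a blocked nose does not count. If painful speech is still wanted for comparability, record it as a separate item. The swallowing and sore-throat definitions can stay as they are.

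The cost is one reworded definition and, if painful speech is kept, one more item on the form; treatment and sample size do not change. The small downside is fewer counted events and less comparability with studies that use the broader wording. The change should be made before data are collected, since a yes/no record made under the present wording cannot later be sorted into voice change and surgical speech trouble.

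### Must the plan state that sore throat is compared on its 0-10 score, with the four severity bands only descriptive?

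*Combined protocol and SAP*

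**What the plan says.** All the relevant text is in the combined protocol and SAP, towards the end of Outcome Measures.

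- Timing: "Sore throat, nausea, vomiting, dysphonia and dysphagia will be evaluated and recorded at 2, 4, 6, 12 and 24 hours postoperatively".
- Definition: "Sore-throat; it was defined as constant pain felt independently of swallowing".
- Scale: "The evaluation was made with 0 ile10 numerical pain rating scale (NRS: Numeric Rating Scala".
- Bands: "According to NRS, sore throat score will be evaluated as; 0-1: none, 2-4: mild, 5-7: intermediate and 8-10: severe".

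These lines belong to a list of definitions of adverse effects, which also covers laryngospasm, bronchospasm, dysphonia, difficulty in swallowing, nausea and vomiting, and cough.

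The Statistical Analyzes section holds only a sample-size statement. It gives "Type I error (alpha) 0.05, the power of the test (1-beta) 0.9", says that "the alternative hypothesis (H1) is two-way", and names "the primary output variable in the air (glottis / trachea) for the amount of blood effect of 0.71". The result is 40 patients per group. No test, summary or model is given there for sore throat, or for any other outcome, the primary one included.

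**The concern.** An eleven-point score is collected, and the only rule for evaluating it reduces it to four grades. The lowest grade treats a score of 1 as no sore throat. If those grades were compared between groups, 0 and 1 would be tied, and so would 2, 3 and 4. Grouping an ordered score usually costs power. Sore throat has no sample size of its own, so its power is whatever 40 per group provides.

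Two further worries follow. If the form held only the grade, the score could not be recovered. If both were held, an analyst could choose among the score, the grades, and none versus any after seeing the results. Sore throat is a patient-reported comparison of the two airway devices, so neither worry is idle.

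**Working it through.** **1. The plan's own figure.** Inputs from Statistical Analyzes: effect 0.71 (read as a standardised difference), two-sided alpha 0.05, power 0.90. By the normal approximation:

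n per group = 2(1.960 + 1.282)² / 0.71² = 41.7, so 42, against 40 stated.

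Power at 40 = Φ(0.71 × √(40/2) − 1.960) = Φ(1.215) = 0.888, against 0.90 stated.

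The figure reproduces approximately. It concerns blood in the airway, and no choice about sore throat alters it.

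**2. Score versus bands.** The documents give no sore-throat distribution, so every distribution below is an assumption. Setting: 40 per group, one time point, two-sided 0.05, Mann-Whitney test with tie and continuity corrections, 20,000 runs per case (simulation standard error at most √(0.25/20,000) = 0.0035). Rejection under three null cases was 0.046-0.049. Scores are rounded and limited to 0-10. A positive last column means that the bands lose power.

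| Assumed scores | Score | Bands | Loss (points) |
|---|---|---|---|
| Spread, mean 0.5 vs 1.8, SD 2.0 | 0.753 | 0.661 | 9.2 |
| Spread, 2 vs 3.5, SD 2.2 | 0.823 | 0.768 | 5.5 |
| Clustered, 2.4 vs 3.1, SD 1.0 | 0.832 | 0.574 | 25.8 |
| 25% vs 55% sore, scores uniform 1-3 | 0.761 | 0.531 | 23.0 |
| 25% vs 55% sore, uniform 1-6 | 0.760 | 0.649 | 11.1 |
| 30% vs 60% sore, scores from 1 up, mean 2, SD 1.2 | 0.737 | 0.492 | 24.5 |
| 30% vs 60% sore, from 1 up, mean 4, SD 1.5 | 0.729 | 0.711 | 1.8 |
| 40% vs 60% sore, from 1 up, means 3 vs 4, SD 1.5 | 0.663 | 0.664 | −0.1 |
| 30% vs 50% sore, from 1 up, means 2.5 vs 3.5, SD 1.5 | 0.602 | 0.636 | −3.4 |
| 30% vs 60% sore, uniform 2-4 | 0.738 | 0.798 | −6.0 |
| Same, 40% of the others report a stray 1 | 0.676 | 0.798 | −12.2 |

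Across all the cases run, the result goes from a loss of about 26 points to a gain of about 12.

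**3. Why the sign changes.** In two of the cases the bands reduce to none versus mild, and a two-proportion approximation shows the mechanism:

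Power ≈ Φ{[d − 1.960 √(2p̄(1−p̄)/40)] / √[(p₁(1−p₁) + p₂(1−p₂))/40]}, where d = p₂ − p₁ and p̄ is their mean.

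- *Sore scores 2-4, 30% vs 60%.* The bands keep the whole difference: Φ[(0.300 − 0.218)/0.1061] = Φ(0.773) = 0.78 (simulated 0.798). The ranking within 2-4 is the same in both groups, so keeping it adds only noise to the score test.
- *Sore scores 1-3, 25% vs 55%.* The bands call one third of sore patients unaffected, leaving 16.7% vs 36.7%: Φ[(0.200 − 0.194)/0.0963] = Φ(0.064) = 0.53 (simulated 0.531).

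Where the sore scores lie matters, and so do any severity difference between groups and the frequency of stray 1s. No single one of these decides the matter. With sore patients scoring 1 or more throughout, the table still runs from a loss of 24.5 points to a gain of 3.4.

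**4. Other uses of the bands.** For rounded normal scores with SD 1.5 and a 1-point difference (1,500 runs per case), power was 0.80-0.82 on the score, 0.69-0.74 for a rank test on the bands, and 0.54-0.60 for a chi-square test on the bands. Over the whole set of normal cases, none versus any ranged from 0.00 to 0.86. The plan proposes none of these tests.

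**The case for a change.** The best case for a change is that it would cost one sentence and one instruction to record the number. In most of the assumed distributions the score does better, and the largest loss from banding (about 26 points) exceeds the largest gain (about 12). A chi-square test on the bands would lose more. Naming the variable in advance has value whatever the distribution turns out to be.

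Some of this stands. The analysed variable is not written down, and the score with a rank-based or ordinal method is a reasonable default.

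Three things take the force out of it.

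- The loss is conditional on a banded test that the protocol does not declare. A 0-10 rating followed by a key to what the numbers mean is an ordinary way to present the scale, and is consistent with the descriptive use that the concern itself asks for.
- Naming the score leaves five assessment times open. An analyst could still select a time, the worst value or a repeated-measures summary, so the sentence would not close off post hoc choice.
- The absence of a stated analysis is general to the plan. Singling out one secondary symptom does not address it.

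**Conclusion.** The concern does not call for a change. What is missing is the name of the analysed variable for one non-primary outcome. That is a gap an analyst would ordinarily fill by comparing the recorded score and tabulating the bands. It is not a stated rule that yields a wrong result.

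The expected gain from stipulating the score is uncertain in sign: compared with a rank test on the bands, it could gain about 26 points of power or give up about 12. These limits rest on assumed distributions at a single time point with 40 per group and would shift with other assumptions. The primary outcome, the 40 per group and the conduct of the trial are unaffected under any of them.

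The remaining risk is that the form holds only the grade. The protocol says that the evaluation is made on the 0-10 scale and gives no sign that the number is discarded.
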